**3.1.1.2. Systemic Events (Systemic Event Symptoms and Fever)**

The systemic events assessed and recorded in the e-diary are fever, decreased appetite, drowsiness/increased sleep, and irritability from Day 1 through Day 7, where Day 1 is the day of each dose. CCI

[Redacted] Maximum temperature range over the period from Day 1 through Day 7 will be mapped into the ranges described in Table 5 for summary of maximum temperature.

The systemic events of decreased appetite, irritability, and drowsiness/increased sleep will be assessed by participants’ parents/legal guardians as mild, moderate, or severe according to the grading scale in Table 4. Grade 4 will not be collected in the e-diary but will be collected as an AE on the CRF.

**Table 4. Grading Scales for Systemic Events**

Systemic Event	Mild Grade 1	Moderate Grade 2	Severe Grade 3	Grade 4 a
Decreased appetite (loss of appetite)	Decreased interest in eating	Decreased oral intake	Refusal to feed	Emergency room visit or hospitalization for severe decreased appetite (loss of appetite)
Drowsiness (increased sleep)	Increased or prolonged sleeping bouts	Slightly subdued interfering with daily activity	Disabling not interested in usual daily activity	Emergency room visit or hospitalization for severe drowsiness (increased sleep)
Irritability (fussiness) (synonymous with restless sleep; decreased sleep)	Easily consolable	Requiring increased attention	Inconsolable; crying cannot be comforted	Emergency room visit or hospitalization for severe irritability (fussiness)

Abbreviation: CRF = case report form.

- a. Grade 4 assessment should be made by the investigator. Grade 4 will not be collected in the e-diary but will be collected as an AE on the CRF. The severity of the systemic event should be graded using the AE severity grading scale.

Temperatures (axillary) will be recorded in degrees for reporting. Fever will be grouped into ranges for the analysis according to Table 5.

[Redacted]

[Redacted]

**Table 5. Ranges for Fever**

≥37.5°C to 38.4°C
>38.4°C to 38.9°C
>38.9°C to 40.0°C
>40.0°C

**Note:** Fever is defined as temperature ≥37.5°C.

CCI [REDACTED]

[REDACTED]

C [REDACTED]

**3.1.1.4. Adverse Events**

AEs will be categorized according to MedDRA terms. AEs will be assessed from the time of informed consent through 1 month after Dose 3 (Visit 4) and from Dose 4 (Visit 5) through 1 month after Dose 4 (Visit 6).

The AE endpoints will be summarized by system organ class and preferred term on a participant level.

This safety endpoint will be supported by summaries and listings of related AEs, severe AEs, and immediate AEs (within the first 30 minutes after each dose).

AE reporting will be based on the specific reporting period. Missing AE start dates will be imputed following the Pfizer data standard rules as described in [Section 5.3](#).

A 3-tier approach will be used to summarize AEs from Dose 1 through 1 month after Dose 3 and, separately, from Dose 4 through 1 month after Dose 4. Under this approach, AEs are classified into 1 of 3 tiers. Different analyses will be performed for different tiers (see [Section 6.1.1.3.1](#)).

- Tier 1 events: These are prespecified events of clinical importance and are identified in a list in the product’s Safety Review Plan. No Tier 1 events have been identified to date for 20vPnC.
- Tier 2 events: These are events that are not Tier 1, but are “common.” A MedDRA preferred term is defined as a Tier 2 event if there are at least 4 participants with the AE term in at least 1 vaccine group.
- Tier 3 events: These are events that are neither Tier 1 nor Tier 2.

[REDACTED]

[REDACTED]

### 3.1.1.5. Serious Adverse Events and Newly Diagnosed Chronic Medical Conditions

SAEs and NDCMCs will be categorized according to MedDRA terms. NDCMCs and SAEs will be collected from the signing of the ICD through the end of the study.

### 3.1.2. Primary Immunogenicity Endpoints

- Pneumococcal serotype-specific IgG concentration 1 month after Dose 3

Concentrations of anticapsular IgG for the 20 pneumococcal serotypes (1, 3, 4, 5, 6A, 6B, 7F, 9V, 14, 18C, 19A, 19F, 23F, 8, 10A, 11A, 12F, 15B, 22F, and 33F) will be determined and classified based on predefined serotype-specific IgG concentrations in all participants at 1 month after Dose 3 using the Luminex assay. The Luminex assay has been validated for the 13vPnC serotypes and the reference concentrations have been bridged to the WHO ELISA, and the predefined IgG concentrations are defined below.

Serotypes	Reference Concentration (µg/mL)
1, 3, 4, 6A, 7F, 9V, 14, 18C, 19F, 23F	≥0.35
5	≥0.23
6B	≥0.10
19A	≥0.12
8, 10A, 11A, 12F, 15B, 22F, 33F	≥0.35

## 3.2. Secondary Endpoints

### 3.2.1. Secondary Immunogenicity Endpoints

- Pneumococcal serotype-specific IgG concentrations 1 month after Dose 3
- Pneumococcal serotype-specific IgG concentrations 1 month after Dose 4
- Pneumococcal serotype-specific OPA titers 1 month after Dose 3, before Dose 4, and 1 month after Dose 4
- Fold changes in pneumococcal serotype-specific IgG concentrations from 1 month after Dose 3 to before Dose 4, from before Dose 4 to 1 month after Dose 4, and from 1 month after Dose 3 to 1 month after Dose 4

#### 3.2.1.1. OPA Titers

OPA titers will be determined on serum from randomly selected subsets of participants provided by an unblinded statistician. The random selection will ensure that each subset has equal representation of both vaccine series. Further details of the subsetting will be described in a memo to the unblinded statistician before any testing proceeds.

CCI

### 3.4.3. Prior/Concomitant Vaccines and Concomitant Medications

The participant will receive investigational product with the specific concomitant vaccines as shown in Table 6.

**Table 6. Vaccination Schedule for Investigational Product and Specified Concomitant Vaccines**

Visit Number	Visit 1	Visit 2	Visit 3	Visit 5
Study Vaccination a	Dose 1	Dose 2	Dose 3	Dose 4
Visit Window	2 Through 6 Months of Age	4 to 8 Weeks After Visit 1	4 to 8 Weeks After Visit 2 (Completed by 12 Months of Age)	12 to 15 Months of Age (≥60 Days After Dose 3)
Investigational product (20vPnC or 13vPnC)	X	X	X	X
Specified concomitant vaccines				
Hib vaccine	X (Vax 1)	X (Vax 2)	X (Vax 3)	X (Vax 4)
HBV vaccine b	X (Vax 1)	X (Vax 2)		
Rotavirus vaccine	X (Vax 1)	X (Vax 2)	X c (Vax 3)	
DTaP-IPV b		X (Vax 1)	X (Vax 2)	X (Vax 4)
MR combination vaccine d				X (Vax 1)
Varicella vaccine d				X (Vax 1)

Abbreviations: DTaP-IPV = diphtheria, tetanus, and acellular pertussis; and inactivated polio combination vaccine; HBV = hepatitis B virus; Hib = *Haemophilus influenzae* type b; MR = measles and rubella; Vax = vaccination.

- Doses of vaccines to be administered at Visits 1 to 3 will be preferred to be administered at 2, 3, and 4 months of age consistent with the recommended vaccination schedule.
- Dose 3 of DTaP-IPV and HBV vaccine will be administered according to the vaccination schedule defined in the labeling. These vaccines will be administered between the blood sample collection 1 month after Dose 3 (Visit 4) and 14 days before Dose 4 (Visit 5).
- Dose 3 for pentavalent rotavirus vaccine only.
- Dose 2 of MR combination vaccine and varicella vaccine will be administered according to the vaccination schedule defined in the labeling.

Other vaccines licensed for this age group may be administered as specified in the protocol. Concomitant medications will be recorded only if they were used to treat SAEs and NDCMCs. Concomitant and prior vaccines and concomitant medications will be coded using the WHO Drug Dictionary.

### 3.5. Safety Endpoints

Local reactions, systemic events, AEs, SAEs, and NDCMCs have been described above (Section 3.1.1) in the primary safety endpoints.

### 4. ANALYSIS SETS (POPULATIONS FOR ANALYSIS)

Analysis populations are defined for the statistical analysis of safety and immunogenicity results in the table below. For the specified criteria in each population definition that are not associated with unblinded information (vaccination as randomized or as actually received), data for all participants will be assessed to determine if participants meet the criteria for inclusion in each analysis population prior to unblinding and releasing the database for the specified analysis and classifications will be documented per standard operating procedures.

Population	Description
Enrolled	All participants who sign the ICD.
Randomized	All participants who are assigned a randomization number in the IRT system.
Dose 3 evaluable immunogenicity	
All participants who
 
 
are eligible and randomized
 
are 2 to 6 months of age (defined as the first day the participant is 2 months of age to the last day the participant is 6 months of age) at the first vaccination
 
receive the first 3 vaccinations to which they are randomized
 
have at least 1 valid immunogenicity result within 27 to 56 days, inclusive, after Dose 3
 
have no other major protocol deviations as determined by the clinician
 
 
The Dose 3 evaluable immunogenicity population will be the primary analysis population for the immunogenicity results from the blood collected up to before Dose 4. Participants will be grouped as randomized in the immunogenicity analysis.

Dose 4 evaluable immunogenicity	
All participants who
 
 
are eligible and randomized
 
are 2 to 6 months of age (defined as the first day the participant is 2 months of age to the last day the participant is 6 months of age) at the first vaccination
 
receive all 4 vaccinations as randomized, and are 12 to 15 months of age (also at least 60 days after Dose 3)
 
have at least 1 valid immunogenicity result within 27 to 56 days, inclusive, after Dose 4
 

Population	Description
	
5. have no other major protocol deviations as determined by the clinician
 
The Dose 4 evaluable immunogenicity population will be the primary analysis population for the pneumococcal immunogenicity results 1 month after Dose 4. Participants will be grouped as randomized in the immunogenicity analysis

[REDACTED]
	
CCI [REDACTED]


Safety
	
All participants who receive at least 1 dose of the investigational product with safety follow-up after any dose.
 
Safety data after Dose 4 will be summarized on the subset of the safety population who also receive Dose 4 with safety follow-up after Dose 4.
 
The statistical analysis of e-diary results will be based on the safety population among those with any e-diary data collected after the specified vaccination.
 
Participants will be grouped according to the vaccine (route) as administered in the safety analysis with safety population.

For the Dose 3 and Dose 4 evaluable immunogenicity population definitions, the blood collection window has been expanded by 1 extra day before and 14 days after the protocol-specified blood collection window of 28 to 42 days defined in the protocol, for consistency with established rules in the Prevenar 13 development program. A major protocol deviation is a protocol deviation that, in the opinion of the sponsor’s clinician, would materially affect assessment of immunogenicity, eg, participant receipt of a prohibited vaccine or medication that might affect immune response or a medication error with suspected decrease in potency of the vaccine. The sponsor’s clinician will identify those participants with major protocol deviations before any unblinded analysis.

For data from participants who receive the incorrect vaccine (route) by mistake, the results will be included in the summary up to the last correct vaccine (route) received in specified reporting time frame and/or dose. Data from all participants will be listed in the listing including those who receive the incorrect vaccine (route) due to errors.

CCI [REDACTED]

[REDACTED]

[REDACTED]

## 5. GENERAL METHODOLOGY AND CONVENTIONS

Statistical analyses are planned to be carried out when the data for the final analyses are available.

### 5.1. Hypotheses and Decision Rules

#### 5.1.1. Immunogenicity Hypotheses

##### 5.1.1.1. Percentage of Participants With Predefined Pneumococcal Serotype-Specific IgG Concentration 1 Month After Dose 3 (Primary Immunogenicity Objectives)

Hypothesis testing will be used to assess the NI of 20vPnC SC to 13vPnC SC for percentages of participants with predefined pneumococcal serotype-specific IgG concentrations 1 month after Dose 3 (see [Section 3.1.2](#) for predefined concentrations). The null hypothesis ( $H_{0A}$ ) for a serotype is

$$H_{0A}: \pi_{20vPnC\ SC} - \pi_{13vPnC\ SC} \leq -10\%,$$

with a 10% margin for NI, where

- $\pi_{20vPnC\ SC}$  is the percentage of participants achieving the IgG concentration of predefined level in the 20vPnC SC group for the serotype 1 month after Dose 3.
- If the serotype is from the 13 matched serotypes (1, 3, 4, 5, 6A, 6B, 7F, 9V, 14, 18C, 19A, 19F, 23F) in 13vPnC,  $\pi_{13vPnC\ SC}$  is the percentage of participants achieving the predefined IgG concentration level for the serotype from the 13vPnC SC group 1 month after Dose 3.
- If the serotype is from the 7 additional serotypes (8, 10A, 11A, 12F, 15B, 22F, 33F) in 20vPnC,  $\pi_{13vPnC\ SC}$  is the percentage of participants achieving a predefined IgG concentration level from the serotype with the lowest percentage 1 month after Dose 3 among the 13 serotypes from the 13vPnC SC group, provided that the lowest percentage is not from serotype 3. If the lowest percentage in the 13vPnC SC group is from serotype 3, the next lowest percentage in the 13vPnC SC group will be used in the comparison. Historical data suggest that serotype 3 behaves somewhat differently from the other serotypes in 13vPnC; therefore, IgG results from serotype 3 will not be used in the comparison to assess the NI of the 7 additional serotypes.

The null hypothesis ( $H_{0A}$ ) will be rejected and NI of the 20vPnC SC group to the 13vPnC SC group for the percentage of participants with the predefined IgG concentration level will be declared for a serotype if the lower bound of the 2-sided 95% CI for the difference (20vPnC SC group – 13vPnC SC group) in percentages, based on the Miettinen and Nurminen method, is greater than –10% (10% NI margin).

### 5.1.1.2. Pneumococcal Serotype-Specific IgG GMCs 1 Month After Dose 3 (Secondary Immunogenicity Objectives)

Hypothesis testing will be used to assess NI of 20vPnC SC to 13vPnC SC for pneumococcal serotype-specific IgG GMCs 1 month after Dose 3. The null hypothesis ( $H_{0B}$ ) for a serotype is

$$H_{0B}: \ln(\mu_{20vPnC\ SC}) - \ln(\mu_{13vPnC\ SC}) \leq \ln(0.5)$$

where  $\ln(0.5)$  corresponds to a 2-fold margin for NI and

- $\ln(\mu_{20vPnC\ SC})$  is the natural log of the geometric mean IgG concentration in the 20vPnC SC group for that serotype 1 month after Dose 3.
- If the serotype is from the 13 matched serotypes (1, 3, 4, 5, 6A, 6B, 7F, 9V, 14, 18C, 19A, 19F, 23F),  $\ln(\mu_{13vPnC\ SC})$  is the natural log of the geometric mean IgG concentration in the 13vPnC SC group 1 month after Dose 3.
- If the serotype is from the 7 additional serotypes (8, 10A, 11A, 12F, 15B, 22F, 33F) in 20vPnC,  $\ln(\mu_{13vPnC\ SC})$  is the natural log of the geometric mean IgG concentration for the serotype with the lowest IgG GMC 1 month after Dose 3 among the 13 serotypes from the 13vPnC SC group, provided that the lowest GMC is not from serotype 3. If the lowest GMC in the 13vPnC SC group is from serotype 3, the next lowest GMC in the 13vPnC SC group will be used in the comparison. As stated in [Section 5.1.1.1](#), historical data suggest that serotype 3 behaves somewhat differently from the other serotypes in 13vPnC; therefore, IgG results from serotype 3 will not be used in the comparison to assess the NI of the 7 additional serotypes.
- The null hypothesis ( $H_{0B}$ ) will be rejected and NI of the 20vPnC SC group to the 13vPnC SC group for the pneumococcal serotype-specific IgG GMC will be declared for a serotype if the lower bound of the 2-sided 95% CI for the IgG GMR of the 20vPnC SC group to the 13vPnC SC group is greater than 0.5 (2-fold NI margin).

## 5.2. General Methods

Time points for local reactions and systemic events refer to data within 7 days after each dose.

CI for all endpoints in the statistical analysis will be presented as 2-sided at the 95% level.

### 5.2.1. Analyses for Binary Data

Descriptive statistics for categorical variables (eg, proportions) are the percentage (%), the numerator (n) and the denominator (N) used in the percentage calculation, and the 95% CI where applicable.

The exact 95% CI for binary endpoints for each group will be computed using the F distribution (Clopper-Pearson). The 95% CI for the between-group difference for binary endpoints will be calculated using the Miettinen and Nurminen method.

The 3-tier approach will be used to summarize AEs. For both Tier 1 (if any are identified during the study) and Tier 2 events, a 95% CI for the between-group difference in proportions will be calculated based on the Miettinen and Nurminen method. In addition, for Tier 1 events (if any), the asymptotic p-values will also be presented for the difference in proportions, based on the same test statistic and under the assumption that the test statistic is asymptotically normally distributed. For Tier 3 events, counts and percentages for each vaccine group will be provided.

### **5.2.2. Analyses for Continuous Data**

Unless otherwise stated, descriptive statistics for continuous variables are n, mean, median, standard deviation, minimum, and maximum.

#### **5.2.2.1. Geometric Means**

For immunogenicity results of serotype-specific IgG concentrations and OPA titers, the geometric means will be computed along with associated 95% CIs. The geometric mean and associated 2-sided 95% CI will be calculated as the mean of the assay results on the natural logarithmic scale based on the Student's t-distribution, and then exponentiating the results.

#### **5.2.2.2. Geometric Mean Ratios**

Where appropriate, GMRs and their 2-sided 95% CIs will be derived by calculating differences in means and CIs on the natural log scale of the assay results based on the t-distribution (allowing for unequal variances), and then exponentiating the results. The difference in means, on the natural log scale, will be the 20vPnC SC group minus the 13vPnC SC group, or the 20vPnC IM group minus the 20vPnC SC group.

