#### 4.1.2. Approximate Number of Participants

Approximately 666 participants will be enrolled to achieve a target of 600 evaluable participants (200 in each vaccine group) at the follow-up time point 1 month after Dose 3.

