### **6.3. Measures to Minimize Bias: Randomization and Blinding**

#### **6.3.1. Allocation to Study Intervention**

Participants will be randomized equally to one of the following vaccine groups: (1) 20vPnC SC group, (2) 13vPnC SC group (control vaccine), or (3) 20vPnC IM group.

Allocation of participants to vaccine groups will proceed through the use of an IRT system (IWR). The site personnel (study coordinator or specified designee; either blinded or unblinded) will be required to enter or select information including but not limited to the user's ID and password, the protocol number, and the participant number. The site personnel will then be provided with a vaccine assignment, randomization number, and DU or container number when study intervention is being supplied via the IRT system. The IRT system will provide a confirmation report containing the participant number, randomization number, and DU or container number assigned. The confirmation report must be stored in the site files.

Study intervention will be dispensed at the study visits summarized in the [SoA](#).

Returned study intervention must not be redispensed to the participants.

An otherwise uninvolved third party (unblinded site staff) will be responsible for administration of the study intervention. This includes ensuring that there are no differences in time or effort taken to administer the study intervention and no blinded site staff or participant's parent(s)/legal guardian(s) are able to view the administration (refer to SRM for details).

The study-specific IRT reference manual and IP manual will provide the contact information and further details on the use of the IRT system.

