## **8. STUDY ASSESSMENTS AND PROCEDURES**

The investigator (or an appropriate delegate at the investigator site) must obtain a signed and dated ICD before performing any study-specific procedures.

The date of birth will be collected to critically evaluate the immune response and safety profile by age.

Study procedures and their timing are summarized in the [SoA](#). Protocol waivers or exemptions are not allowed.

Safety issues should be discussed with the sponsor immediately upon occurrence or awareness to determine if the participant should continue or discontinue study intervention.

Adherence to the study design requirements, including those specified in the [SoA](#), is essential and required for study conduct.

All screening evaluations must be completed and reviewed to confirm that potential participants meet all eligibility criteria. The investigator will maintain a screening log to record details of all participants screened and to confirm eligibility or record reasons for screening failure, as applicable.

Every effort should be made to ensure that protocol-required tests and procedures are completed as described. However, it is anticipated that from time to time there may be circumstances outside the control of the investigator that may make it unfeasible to perform the test. In these cases, the investigator must take all steps necessary to ensure the safety and well-being of the participant. When a protocol-required test cannot be performed, the investigator will document the reason for the missed test and any corrective and preventive actions that he or she has taken to ensure that required processes are adhered to as soon as possible. The study team must be informed of these incidents in a timely manner.

For samples being collected and shipped, detailed collection, processing, storage, and shipment instructions and contact information will be provided to the investigator site prior to initiation of the study.

The total blood sampling volume for individual participants in this study is approximately 15 mL.

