## 9.4. Statistical Analyses

The SAP will be developed and finalized before database lock for any of the planned analysis in [Section 9.5](#). The SAP will describe the participant populations to be included in the analyses, and procedures for accounting for missing, unused, and spurious data. This section is a summary of the planned statistical analyses of the primary, secondary, CCI [REDACTED] endpoints.

All CIs in the statistical analysis will be calculated as two-sided at 95% level.

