	
For each of the 20 serotypes for 20vPnC IM and 20vPnC SC groups, difference (20vPnC IM - 20vPnC SC) and the 2-sided 95% CI for the percentage of participants with predefined serotype-specific IgG concentrations 1 month after Dose 3 will be provided.
 
The Miettinen and Nurminen method will be used to derive the CI for the difference in percentages between vaccine groups.
 
The analysis will be based on the Dose 3 evaluable immunogenicity population. An additional analysis will be performed based on the Dose 3 all-available immunogenicity population if there is a large enough difference in sample size between the all-available immunogenicity population and the evaluable immunogenicity population. Participants will be summarized according to the vaccine group to which they were randomized. Missing serology data will not be imputed.

Secondary immunogenicity	
 
 
• GMRs of pneumococcal serotype-specific IgG concentrations 1 month after Dose 3
 
For each of the 20 serotypes, the GMR of 20vPnC SC to 13vPnC SC at 1 month after Dose 3 will be provided. GMRs and their 2-sided 95% CIs will be derived by calculating differences in means and CIs on the natural log scale based on the Student's t-distribution, then exponentiating the results. The difference in means, on the natural log scale, will be 20vPnC SC -13vPnC SC.
 
Hypothesis testing for noninferiority of 20vPnC SC to 13vPnC SC will be performed as described in Section 9.1.2.2.
 
For each of the 20 serotypes, the GMR of 20vPnC IM to 20vPnC SC at 1 month after Dose 3 will be provided.
 
 
 
• GMCs of pneumococcal serotype-specific IgG concentrations 1 month after Dose 4
 
For each of the 20 serotypes, GMCs and 2-sided 95% CIs for pneumococcal serotype-specific IgG concentrations at 1 month after Dose 4 will be provided for each group. Geometric means and the associated 2-sided 95% CIs will be derived by calculating means and CIs on the natural log scale based on the Student's t-distribution, and then exponentiating the results.
 
 

Endpoint	Statistical Analysis Methods

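### The main IgG GMR analysis is valid but makes no use of age at Dose 1; prespecifying age adjustment would add modest precision and needs no new data

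*SAP*

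**What the plan says.** **Method.** SAP 5.2.2.2 obtains the GMR as a difference in mean log concentration, with an interval "based on the t-distribution (allowing for unequal variances". SAP 6.2.1.1.1 applies this at 1 month after Dose 3, in the Dose 3 evaluable population, to 20vPnC SC against 13vPnC SC and to 20vPnC IM against 20vPnC SC. Protocol 9.4.1 has the ratios "derived by calculating differences in means and CIs on the natural log scale based on the Student's t-distribution, then exponentiating the results". None of these sections names a covariate.

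**Status.** The SC comparison is a secondary noninferiority objective (SAP 5.1.1.2, "Pneumococcal Serotype-Specific IgG GMCs 1 Month After Dose 3 (Secondary Immunogenicity Objectives"). It is met for a serotype when the lower limit "is greater than 0.5 (2-fold NI margin". Protocol 9.4 sets the level: "All CIs in the statistical analysis will be calculated as two-sided at 95% level". The IM to SC ratio is a secondary description.

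**Age.** Entry is allowed from 2 through 6 months (Protocol 4.1 and 5.1). Protocol 8 states: "The date of birth will be collected to critically evaluate the immune response and safety profile by age". On allocation, Protocol 6.3.1 says "Participants will be randomized equally to one of the following vaccine groups" and names no age strata. Protocol 6.1.1 prefers Doses 1 to 3 at 2, 3 and 4 months. In the visible SAP, age is used in the analysis-set definitions and the demographic summary.

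**Size.** Protocol 4.1.2: "Approximately 666 participants will be enrolled to achieve a target of 600 evaluable participants (200 in each vaccine group".

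**The concern.** The protocol itself treats age as relevant to the immune response, lets entry age vary over several months, and records date of birth for every infant. If age at Dose 1 predicts IgG after Dose 3, an unadjusted two-sample interval leaves that variation in the error term. Any chance age difference between groups then adds to the sampling error of the ratio. Age at Dose 1 is set by birth and enrolment, not by the vaccine received, so it is a legitimate covariate. On the log scale a linear model still targets the difference in mean ln(IgG), so the GMR keeps its meaning.

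At stake is the width of the intervals for the SC noninferiority ratios and for the IM to SC ratios, which have no formal test and are read from their intervals. In addition, the evaluable population is selected after randomisation by doses received, sampling window and deviations. Randomisation therefore does not fully guarantee age balance in the set that is analysed.

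**Working it through.** **Inputs.** From the documents: 200 evaluable per group, two-sided 95% intervals, margin ln(0.5) = −0.693. Not in the visible documents, so assumed: SD of ln(IgG) 0.8 to 1.5; R² of age with ln(IgG) 0.02 to 0.20; age at Dose 1 either uniform over 2 to 7 months (up to the last day of month 6) or concentrated with SD 0.5 month.

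**1. The plan's own figures.** The visible text gives no power or precision for the GMR. Table 6 of the protocol (92% at 200 per group) concerns the percentage endpoint across all 20 serotypes. It was simulated from inputs that are not visible, so it cannot be rebuilt and does not bear on this point. The sample size is consistent: 666/3 = 222 and 600/3 = 200, a loss of 66/666 = 9.9%.

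**2. Unadjusted interval.** SE = SD × √(2/200) = 0.1 × SD. The limits are the GMR divided and multiplied by exp(t × 0.1 × SD), with t = 1.966 on 398 df. The factor is 1.17, 1.22, 1.27 and 1.34 for SD 0.8, 1.0, 1.2 and 1.5.

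**3. Effect of adjustment on width.** The residual SD becomes SD × √(1 − R²), and the equivalent group size is 200/(1 − R²).

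| R² | Width factor | Equivalent n per group |
|---|---|---|
| 0.02 | 0.990 | 204 |
| 0.05 | 0.975 | 211 |
| 0.10 | 0.949 | 222 |
| 0.20 | 0.894 | 250 |

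A simulation with SD 1.0 gave mean standard errors of 0.100 unadjusted and 0.0975, 0.095 and 0.0895 adjusted at R² 0.05, 0.10 and 0.20, which matches these factors.

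**4. Effect on noninferiority power per serotype.** Noncentral t with noncentrality [ln(GMR) + ln 2] / [SD × √(1 − R²) × √(2/200)]. Example: GMR 0.7 and SD 1.2 give (−0.357 + 0.693)/0.12 = 2.80 and power 79.9%. At R² 0.10 the denominator is 0.1138, the noncentrality 2.96 and the power 83.9%.

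| True GMR | SD | Unadjusted | R² 0.05 | R² 0.10 | R² 0.20 |
|---|---|---|---|---|---|
| 1.0 | 1.5 | 99.6% | 99.7% | 99.8% | 99.9% |
| 0.8 | 1.2 | 97.4% | 98.0% | 98.5% | 99.2% |
| 0.7 | 1.2 | 79.9% | 81.9% | 83.9% | 87.9% |
| 0.7 | 1.5 | 60.9% | 63.2% | 65.5% | 70.6% |

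**5. Chance imbalance.** Uniform age has SD 5/√12 = 1.44 months. The 95% range of the difference in mean age is then ±1.96 × 1.44 × 0.1 = ±0.28 month; with SD 0.5 it is ±0.10 month. The matching downward shift in the GMR is exp(−1.96 × √R² × SD × 0.1). At SD 1.0 this is 0.973, 0.957, 0.940 and 0.916 for R² 0.02, 0.05, 0.10 and 0.20. It is part of the sampling error that the interval in step 2 already counts.

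**6. Validity.** With true GMR 0.5 and 10,000 simulated trials per setting (SD 1.0 and 1.3, R² 0 to 0.20, uniform age, equal variances), one-sided error was 2.3% to 2.9% for both the unadjusted test and a common-slope age model, against a nominal 2.5%. The interaction model with robust standard errors proposed under the fix was not itself simulated.

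**The case against.** The strongest reply is that nothing is wrong. The planned test holds its error rate, and chance imbalance under randomisation is ordinary sampling error covered by the interval. A reader might infer that age imbalance biases the GMR or invalidates the noninferiority test; steps 5 and 6 do not support that, and this part of the reply stands in full.

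The benefit is also assumed. The documents report no correlation between age and IgG, no SD of ln(IgG) and no expected age distribution. The preference for dosing at 2, 3 and 4 months may concentrate Dose 1 near 2 months, which shrinks R². This stands too: it limits the size of the claim, though not the case for prespecifying the model.

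A reader might also infer that the plan ignores age altogether. The documents cannot show that. Text is blacked out after the GMR methods and main analysis in the SAP, and again between Sections 6.2.1.5 and 6.5, so a by-age or supplementary analysis may exist. The point is confined to the specified main analysis. Nor does the stated purpose of collecting date of birth promise covariate adjustment.

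Nor should the IM to SC GMR be read as the main basis for judging the IM route. The primary IM estimand is the difference in the percentage reaching the IgG threshold; the GMR is secondary.

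Finally, for the 7 additional serotypes the two groups contribute different serotypes, so a single age slope need not fit both, and adjustment could make it unclear which control serotype is lowest. Both objections can be met in the model specification.

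**Conclusion.** The point holds as an optional efficiency improvement on a secondary objective, with no error in the plan. The specified GMR analysis is valid and does not use a baseline variable that the trial already records. For assumed R² of 2%, 5% and 10%, adjustment narrows the log-scale intervals by about 1%, 2.5% and 5%. The true R² is unknown, and the gain is near zero if Dose 1 ages cluster at 2 months.

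It would rarely alter a noninferiority decision when the true GMR is near 1, because power per serotype is then already 99.6% or more over the assumed SDs. A gain of roughly 5 to 10 percentage points in power needs a true GMR near 0.7, a large SD and R² of about 0.10 to 0.20. The documents support none of these. To say that meaningful precision is known to be lost would go beyond them.

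**What to change.** Before unblinding, amend SAP 5.2.2.2, with a matching line in 6.2.1.1.1, as follows:

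- Derive each GMR and its 95% CI from a linear model of ln(IgG) on vaccine group, age at Dose 1 in days centred at the pooled mean, and their interaction, and exponentiate the group coefficient. The interaction lets each group have its own age slope, which the 7 additional serotypes need.
- Use heteroscedasticity-robust standard errors, which keep the present allowance for unequal variances.
- For the 7 additional serotypes, choose the lowest-GMC control serotype (excluding serotype 3) on unadjusted GMCs, so that the choice does not depend on the model.
- Report the unadjusted t-based GMR as support.
- Leave the primary Miettinen and Nurminen analysis of percentages unchanged.

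The timing matters, because adjusting only after an age imbalance has been seen would be post hoc. The cost is SAP wording and one model per serotype and comparison, with no new data. Protocol Section 9 lets the SAP modify the outlined methods and asks for a protocol amendment only for major changes to the primary endpoints or their analyses, which this is not.
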